11.0 HIV-RELATED MEASURES

11.1 Antiretroviral Medication Prescription and Adherence

Since HIV viral suppression is most strongly influenced by optimal use of ART, evaluation of adherence to one's ART regimen is essential. Self-reported antiretroviral use and adherence will be assessed using a Medication Adherence questionnaire with visual analogue scale [142, 143] that is administered at baseline, treatment initiation, and weeks 4, 8, 12, 16, 20 and 24 weeks or the end of study visit (if not week 24) for assessment of secondary outcome if participant is prescribed ART at the time of follow-up visits. The Medication Adherence questionnaire asks the participant about adherence to HIV medications in the past month. We will assess the proportion of participants taking 100% of prescribed ART doses, based on visual analogue scale responses, in the past month at baseline, treatment initiation, and weeks 4, 8, 12, 16, 20, and 24 for those prescribed ART (proportion; self-reported medication adherence measure).

Because self-reported use of specific antiretrovirals has limited reliability when compared with medical record review [144, 145], we will confirm ART use with medical record review at baseline and 24 weeks (or the end of study visit, if not week 24) using the ARV Medication Log to assess the secondary outcome of ART prescription. Specifically, we will assess change in the proportion of participants prescribed ART within 24 weeks following randomization, compared to baseline (binary; medical record abstraction).

11.2 HIV Care Utilization

Study staff will assess the number of HIV primary care visits at baseline and 24 weeks, or the end of study visit, if not week 24 (count, chart abstraction).

11.3 HIV Risk Assessment Battery

The Risk Assessment Battery (RAB) [146] is a self-administered assessment of engagement in activities that increase the likelihood of HIV transmission. Only sexual and drug-related HIV risk behavior items will be included, in an effort to limit instrument redundancy and participant response burden. Several scores that measure drug risk, sex risk, and total risk will be computed. It will be assessed at baseline and at weeks 4, 8, 12, 16, 20, and 24 (or the end of study visit, if not week 24).

11.4 VACS Index

The VACS Index is a validated biomarker score that reflects overall health and is a potent predictor of mortality in HIV-infected patients [147, 148]. The VACS Index is calculated by summing scores for age, CD4 count, HIV-1 RNA, hemoglobin, liver fibrosis (FIB-4), renal function (eGFR), and HCV status (**Table 11.1**) [148, 149]. It is responsive to abstinence among HIV-infected patients receiving opioid agonist treatment even when they enter such treatment with an undetectable HIV viral load [150]. A clinically meaningful difference is 5 points as it relates to a 20% change in 5-year mortality risk [147-149]. It will be assessed at randomization and week 24, or the end of study visit, if not week 24.

11.5 Table 1: Point Values Used to Calculate VACS Index

Component		VACS Index
Age	<50	0
	50-64	12
	≥65	27
CD4	≥500	0
	350 to 499	6
	200 to 349	6
	100 to 199	10
	50 to 99	28
	<50	29
HIV-1 RNA	<500	0
	500-1x10 ⁵	7
	>1x10 ⁵	14
Hemoglobin	≥14	0
	12 to 13.9	10
	10 to 11.9	22
	<10	38
FIB-4	<1.45	0
	1.45 to 3.25	6
	>3.25	25
eGFR	≥60	0
	45 to 59.9	6
	30 to 44.9	8
	<30	26
Hepatitis C		5

Definitions:

- FIB-4 = (years of age x AST in U/L) ÷ (platelets in 10⁹/L x square root of ALT in U/L)
 - Measure of liver fibrosis
- eGFR = 186.3 x (serum creatinine^{-1.154}) x (age^{-0.203}) x (0.742 for women) x (1.21 if black)
 - Estimated glomerular filtration rate; Measure of renal function

12.0 GENERAL MEASURES

12.1 Inclusion/Exclusion

This form will include each inclusion and exclusion criterion to document eligibility. Eligibility will be assessed prior to randomization, and then continually as appropriate. Only participants who continue to meet study eligibility criteria will be allowed to continue with the screening process and randomization.

12.2 Locator Form

A locator form will be used to obtain information to assist in finding participants during screening/baseline and at follow-up. This form will collect participants' current address, email address, and phone number(s). In order to facilitate locating participants if direct contact efforts are unsuccessful, we will attempt to collect addresses and phone numbers of 2-3 family/friends, who may know how to reach the participant, as well as information such as Social Security number, driver's license number, social media, and other information to aid in searches of public records. This information will be collected at screening and will be updated at each visit. No information from this form will be used in data analyses.

12.3 PhenX Core Tier 1 Forms

The Substance Abuse and Addiction Collection of the PhenX Toolkit (www.phenxtoolkit.org) includes highly recommended measures that are being adopted across NIDA-funded research. The Core Tier 1 collection includes measures for demographics (age, ethnicity, sex, race, educational attainment, employment status and marital status), BMI, quality of life, and HIV Risk & Status; substance use measures include age of onset, past 30-day quantity and frequency, lifetime use for alcohol, tobacco and other substances. We will delete Core Tier 1 items regarding HIV testing, since only HIV-infected participants are eligible for the current study. Core Tier 1 assessments will be completed at baseline only, with BMI and tobacco use questions repeated at week 24 or the end of study visit, if not week 24.

12.4 Demographics Form

The demographics form will collect information about demographic characteristics of the participant, including sex, date of birth, ethnicity, race, education, employment pattern, and marital status. The PhenX Core Tier 1 form will be completed during the screening process to collect demographic data.

12.5 Treatment Satisfaction Survey

Satisfaction with treatment will be recorded on the Treatment Satisfaction Survey completed at week 24 visit or the end of study visit, if not week 24.

12.6 Treatment Plan

This form will be used once the participant is randomized. After randomization, the participant will meet with the study clinician to develop a plan that will determine the activities the participant should engage in, including addiction pharmacotherapy (e.g., methadone, buprenorphine, XR-NTX) during the active treatment phase of the protocol. This meeting and form should be completed the same day the participant is randomized. The Treatment Plan will be reviewed at follow-up visits 4, 8, 12, 16, 20, and 24 or the end of study visit, if not week 24.

12.7 Medication Adherence

This form will track the participant's adherence to recommended addiction pharmacotherapy (i.e., methadone, buprenorphine, or XR-NTX) as described in the Treatment Plan.

12.8 End of Treatment Form

This form tracks the participant's status with regards to the study intervention/medication or treatment(s) received as part of TAU. It will be completed if the participant permanently stops treatment early or at the week 24 visit (for participants who complete study participation) or at the end of study visit (for participants who permanently stop the study trial early).

12.9 Study Completion Form

This form tracks the participant's status in the study. It will be completed at the week 24 visit, once the week 24 visit window elapses for participants who do not complete this final visit or after the week 24 visit is completed for participants who complete the final visit, or once the site confirms that a participant is permanently done with the study (i.e., participant died or withdrew consent). This form will be used in data analyses to address variables such as treatment retention and completion.

12.10 Treatment Initiation and XR-NTX Non-Initiation

The Treatment Initiation form will track participants randomized to the TAU arm only and will track initiation of TAU. This form will be completed once the participant reports that they have initiated TAU treatment. If treatment is not initiated, the form must be completed by end of study.

The XR-NTX Non-Initiation form will track non-initiation of XR-NTX injections for participants randomized to the XR-NTX treatment arm. This form will be completed as needed if a participant does not receive any XR-NTX injections. If the participant receives *at least* one injection, this form will not be completed.

13.0 SAFETY AND MEDICAL MEASURES

The study clinician must review and approve all safety and eligibility assessments to confirm participant eligibility prior to randomization.

13.1 Medical and Psychiatric History

The study clinician will obtain a medical and psychiatric history from the participant covering past and present health conditions to help determine eligibility and to provide baseline information. This form will be collected during screening. Information from this form may be used in data analyses.

13.2 Physical Examination

The study clinician will complete a physical examination at screening, to ensure that there are no medical concerns regarding participation and to gather baseline information regarding the participant's physical health. During the screening physical exam, a description of the participant's body habitus will be documented, and the study clinician will examine the planned injection sites to ensure adequacy for XR-NTX gluteal intramuscular injection of naltrexone with the supplied needle.

13.3 Vital Signs

Study personnel will complete vital signs (blood pressure, pulse, temperature, height, and weight) at screening to inform overall medical fitness for participation, along with the physical exam. Height and weight only will be collected at week 24 or the end of study visit, if not week 24.

13.4 DSM-5 Checklist

The DSM-5 Checklist is a semi-structured, interviewer-administered instrument that provides current diagnoses for substance use disorders based on DSM-5 diagnostic criteria. The DSM-5 Checklist will be completed at screening to determine eligibility.

13.5 Clinical Laboratory Tests

Trained staff will be responsible for collecting and processing biologic specimens. Local laboratories at participating sites will be used to conduct all laboratory tests with the exception of the PBMCs. Laboratories must participate in the Clinical Laboratory Improvement Act of 1998 (CLIA) or be accredited by the College of American Pathologists (CAP). If neither CLIA nor CAP is available, equivalent evidence of laboratory certification may be acceptable and must be discussed on a case-by-case basis with the Lead Team. Laboratories should provide reference ranges and proof of laboratory certification.

HIV-1 RNA PCR: will be drawn at screening, 12, and 24 weeks (or the end of study visit, if not week 24) for outcomes assessment. At screening, results of laboratory tests conducted within 90 days prior to date of informed consent will be acceptable.

CD4 Count (T-helper cells): will be drawn at randomization and at 12 and 24 week visits or the end of study visit, if not week 24, for secondary outcomes assessment. At randomization, results of laboratory tests conducted within 90 days prior to date of informed consent will be acceptable.

Peripheral Blood Mononuclear Cells (PBMCs): For all randomized participants (both TAU and XR-NTX), we will collect four 8mL or eight 4mL CPT tubes for PBMC analysis at randomization,

12, and 24 (or end of study visit if not week 24). Blood draws may coincide with other research blood draws. PBMC analysis will be conducted in a related NIH application to assess the effects of opioid blockade on TLR mediated immune responses at a later time. PBMC samples will be shipped to a lab at Oregon Health & Science University and kept indefinitely. PBMC samples will be used for immunologic testing. It is also possible that banked PBMC specimens will be shared with other investigators for performance of genetic testing in the future.

Safety labs: AST, ALT, CBC, INR, serum creatinine, and urine pregnancy test (for all females) will be performed to help determine eligibility at screening. Receipt and review of laboratory test results is necessary before confirming eligibility, conducting randomization and starting study medication. Results of laboratory tests (not including urine pregnancy) conducted within 30 days prior to date of informed consent (e.g., collected as part of routine detoxification admission) will be acceptable. Urine pregnancy test will be repeated at the Treatment Initiation Visit (required for XR-NTX arm only), the safety visit (required for XR-NTX arm only), and weeks 4, 8, 12, 16, 20, and 24 (or the end of study visit, if not week 24). AST, ALT, CBC, INR and serum creatinine will be repeated at week 24 or the end of study visit, if not week 24.

Liver profile: AST, ALT, and INR will be repeated at the Week 12 and Week 24 visits (or the end of study visit, if not Week 24). This is consistent with recent studies supporting the lack of hepatotoxicity in patients receiving XR-NTX that led to dropping of the previous FDA black box warning regarding hepatotoxicity.

Hepatitis: Blood will be collected at randomization for Hepatitis B surface antigen (HBsAG) and Hepatitis C virus antibody (HCVab) with reflex hepatitis C RNA PCR testing if antibody positive. These tests do not determine eligibility. Results of laboratory tests conducted within 90 days prior to date of informed consent (e.g., collected as part of routine detoxification admission) will be acceptable.

13.6 Pregnancy and Birth Control Assessment

This form will document the administration of pregnancy tests, test results, and female participants' self-reports of an acceptable method of birth control. The pregnancy and birth control assessment form, including on-site urine pregnancy tests, will be collected at screening. Birth control assessment and a urine pregnancy test will be repeated at the Treatment Initiation Visit prior to study drug induction (urine pregnancy test required for XR-NTX arm only), the safety visit (urine pregnancy test required for XR-NTX arm only) and the 4, 8, 12, 16, 20, and 24 week visits or the end of study visit, if not week 24. This will correspond to medical visits for repeat study drug dosing and a final assessment at week 24 or the end of study visit, if not week 24.

13.7 Injection Site Examination

The study clinician will examine the injection site on the next visit following each XR-NTX administration and document this on the Injection Site Examination form. The study clinician will also examine the injection site per standard of care before administering a new injection. Participants will be asked to immediately report any injection site reactions to study staff for evaluation, monitoring, and possible referral, as needed. Injection site reactions will be documented on the Injection Site Abnormality Log.

13.8 Pain Assessment

Pain assessment will occur at baseline, 4, 8, 12, 16, 20, and 24 weeks (or the end of study visit, if not week 24). Participants will be assessed for experiences of pain during the past 4 weeks

using the 3-item PEG [151]. The PEG asks respondents to estimate on a scale of 0 to 10 their average pain intensity (P), interference with enjoyment of life (E), and interference with general activity (G). Participants will also be asked how pain was managed.

14.0 SUBSTANCE USE AND MENTAL HEALTH COVARIABLES

14.1 Urine Drug Screen

Urine drug screens will be collected at screening, study drug induction (Treatment Initiation Visit – required for XR-NTX arm only), safety visit (required for XR-NTX arm only), and 4, 8, 12, 16, 20, and 24 weeks (or the end of study visit, if not week 24) for assessment of secondary outcomes. All urine specimens will be collected using FDA-approved one-step temperature-controlled urine drug test cups following all of the manufacturer's recommended procedures. A further validity check will be performed using a commercially available adulterant test strip. The UDS will test for the presence of the following drugs: opiates, oxycodone, barbiturates, benzodiazepines, cocaine, amphetamines, methamphetamines, marijuana, methadone, buprenorphine, phencyclidine (PCP), fentanyl and ecstasy (MDMA). The PCP result will not be recorded in the data system. The UDS will also test for ethyl glucuronide (EtG), which is a biomarker of alcohol consumption in the previous 22 to 31 hours and will be used to confirm self-reported alcohol abstinence [152, 153]. The UDS will be performed using various commercially available single or multi-panel tests. In the event urine specimen tampering is suspected, either based on observation or the adulterant tests, study staff should request a second urine sample, directly observed or according to clinic SOPs.

14.2 Addiction Severity Index-Lite (ASI-Lite) Drug and Alcohol Use

The ASI-Lite is derived from the Fifth Edition of the ASI [154], a structured clinical interview that yields scores for seven areas of functioning typically impacted by addiction, including medical status, employment status, drug use, alcohol use, family status, legal status, and psychiatric status. Only the drug use and alcohol use sections of the ASI-Lite will be used. Opioid use questions, including the main type of opioid used by the participant, whether a prescription opioid or heroin, the onset of the use, the participant's perception of the substance that is most problematic, and their present treatment goal will also be assessed at baseline as part of the ASI-Lite assessment. The ASI-Lite drug and alcohol sections will be completed at baseline and 24 weeks (or the end of study visit, if not week 24) for assessment of secondary outcomes.

14.3 Timeline Follow Back (TLFB)

Timeline Follow Back (TLFB) assesses self-reported drug and alcohol use over the past 30 days, with high test-retest reliability and validity [155, 156]. Participants will be asked to report daily drug and alcohol use in the specified timeframe (e.g., since the last visit). TLFB will be completed at the following visits: baseline, treatment initiation, and weeks 4, 8, 12, 16, 20, and 24 (or the end of study visit, if not week 24) for assessment of secondary outcomes. Baseline TLFB assesses use in the 30 days prior to informed consent through to the date of the baseline visit.

14.4 Visual Analog Craving Scale (VAS)

Participants' craving for opioids, alcohol and tobacco will be documented on a visual analog scale (VAS) that ranges from 0 (no craving) to 100 (most intense craving possible). Participants will be instructed specifically to indicate the overall intensity of craving experienced. This scale will be completed at baseline and at 4, 8, 12, 16, 20, and 24 weeks (or the end of study visit, if not week 24) for assessment of secondary outcomes.

14.5 Treatment Services Review (TSR), Version 6 (28 days)

Select items from the Treatment Services Review, Version 6 (TSR-6) addiction treatment modules will be used to collect data on the number of counseling sessions attended in the past 28 days, as well as detoxification, outpatient, inpatient, and medication-assisted addiction treatment services [157]. Participants will complete a modified TSR-6 at baseline, treatment initiation, and 4, 8, 12, 16, 20, and 24 weeks (or the end of study visit, if not week 24) for assessment of TAU and counseling exposure in both TAU and XR-NTX arms.

14.6 Medication-Assisted Treatment

To assess study drug and other medication-assisted treatment exposure, TSR-6 responses will be augmented regarding use of medications for treatment of addiction with additional items asking specifically about use of methadone, buprenorphine, and extended-release naltrexone during the past 28 days for participants randomized to both TAU and XR-NTX arms. Participants will be asked to report the number of days in the past 28 days that each medication was taken at least once per day. This information will be collected from participants at baseline, treatment initiation, and weeks 4, 8, 12, 16, 20, and 24 (or the end of study visit, if not week 24). Additional information gleaned from medical record review to assess the dose and number of days of treatment prescribed for each medication will further augment this assessment.

14.7 Quality of Life

We will measure quality of life using the EuroQol Group 5D (EQ-5D), a validated, self-reported, 5-item instrument used to measure health-related quality of life in a wide variety of populations. The form will be collected at the baseline and week 24 visit. [158, 159]

14.8 Participant Treatment Preference

We will collect each participant's preference for agonist or antagonist treatment using the Participant Treatment Preference form. This form consists of a single item that collects participant treatment preference on a slider scale of 1-10, with 1 being "strongly prefer buprenorphine or methadone (agonist treatment)," 10 being "strongly prefer extended release naltrexone (antagonist treatment)," and 5 being "no preference." The form will be collected via participant self-report at baseline.

15.0 SAFETY ASSESSMENTS

15.1 Adverse Events, including Serious Adverse Events, and Protocol Deviations

Adverse Events, Serious Adverse Events, and Protocol Deviations will be assessed and documented.

Study staff members will assess for any medical or psychiatric side effects by asking: "How have you been feeling since your last visit?" AEs will be solicited at each study visit but will be recorded at any visit after consent when reported by the participant according to the adverse event reporting definitions and procedures outlined in the protocol.

If a reported AE suggests medical or psychological deterioration, it will be brought to the attention of the study clinician for further evaluation. SAEs will be medically managed, reported, and followed in accordance with applicable regulatory requirements. Safety assessments will be performed at all visits.

15.2 Non-Fatal Overdose

Non-fatal opioid overdoses in the past 4 weeks will be assessed using a self-reported instrument used in previous studies at baseline and 24 weeks (or the end of study visit, if not week 24) [160]. Overdose events are sentinel events that are less likely to be prone to recall bias than other events. If non-fatal overdose resulted in a serious adverse event, it should also be captured on the AE/SAE CRF.

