19.3.1 Adverse Events

For the purposes of this study, mild (Grade 1) and unrelated Adverse Events will not require reporting in the data system. All adverse events will be tracked on a manual (paper only) Adverse Event Log, regardless of severity, seriousness, relatedness, or expectedness.

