19.3.2 Serious Adverse Events

For the purpose of this study, the following events will not be reported as an SAE, but will be recorded on study specific forms in the data system.

- 1) Detox admissions (documented instead on the DTX form).**
- 2) Admission for labor and delivery (documented instead on the Confirmed Pregnancy and Outcomes form).**
- 3) Admission for elective or pre-planned surgery.**

The Lead Node will report all other SAEs on the Serious Adverse Event form in the data system. Sites must determine if local IRBs will require annual or other SAE reporting.

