19.4 Known Potential Toxicities of Study Drug/Intervention

Refer to the package insert for XR-NTX.

19.5 Known Potential Adverse Events Related to the Underlying Clinical Condition and/or Study Populations

Each of the participating research sites has established practices for managing medical and psychiatric emergencies, and the study staff will continue to utilize these procedures. Treatment providers at each research site will be responsible for monitoring participants for possible clinical deterioration or other problems, and for implementing appropriate courses of action.

As this population will have significant ongoing health and substance use issues, events related to complications of HIV, substance use treatment or admission for substance detoxification will be captured on study-specific forms and not duplicitely reported as an adverse or serious adverse event. All hospitalizations for other (non-HIV, non-substance-use related) medical, surgical and psychological reasons and deaths will be reported on AE/SAE forms. These data will still be included in the reports to the DSMB at the regular meetings.

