23.1 Definition of Adverse Events and Serious Adverse Events

An **Adverse Event** (AE) is any untoward medical occurrence in humans, whether or not considered study drug/intervention related which occurs during the conduct of a clinical trial. Any change from baseline in clinical status or any findings from lab results, x-rays, physical examinations, etc., that are considered clinically significant by the study medical clinician are considered AEs.

Suspected adverse reaction is any adverse event for which there is a reasonable possibility that the study drug/intervention caused the adverse event. A reasonable possibility implies that there is evidence that the study drug/intervention caused the event.

Adverse reaction is any adverse event caused by the study drug/intervention.

An **adverse event, suspected adverse reaction, or adverse reaction** is considered “**serious**” (i.e., a serious adverse event, serious suspected adverse reaction or serious adverse reaction) if, in the view of either the study medical clinician or sponsor, it:

- 1) Results in death: A death occurring during the study or which comes to the attention of the study staff during the protocol-defined follow-up period, whether or not considered caused by the study drug/intervention, must be reported.
- 2) Is life-threatening: Life-threatening means that the study participant was, in the opinion of the medical clinician or sponsor, at immediate risk of death from the reaction as it occurred and required immediate intervention.
- 3) Requires inpatient hospitalization or prolongation of existing hospitalization.
- 4) Results in persistent or significant incapacity or substantial disruption of the ability to conduct normal life functions. Is a congenital abnormality or birth defect.
- 5) Important medical event that may not result in one of the above outcomes, but may jeopardize the health of the study participant or require medical or surgical intervention to prevent one of the outcomes listed in the above definition of serious event.

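### After baseline the only structured non-fatal overdose question is asked once with a 4-week look-back (4 of 24 weeks), and Section 19.5 conflicts with 19.3.2 on reporting HIV-related hospitalizations and is ambiguous on overdose ones

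*Combined protocol and SAP*

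**What the plan says.** **Overdose question.** Section 15.2: "Non-fatal opioid overdoses in the past 4 weeks will be assessed using a self-reported instrument used in previous studies at baseline and 24 weeks", or at the end-of-study visit when that is not week 24. Section 6.2 sets 24 weeks of treatment with visits every 4 weeks. Columns in the Section 10.1 schedule are displaced in the extracted text. However, the overdose row carries the same marks as ASI-Lite, which Section 14.2 places at baseline and at week 24 or end of study.

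**Other capture routes.**
- Section 15.1 has an open, non-specific AE prompt at each visit.
- Section 19.3.1: "All adverse events will be tracked on a manual (paper only) Adverse Event Log, regardless of severity, seriousness, relatedness, or expectedness". The same section says that "mild (Grade 1) and unrelated Adverse Events will not require reporting in the data system".
- Section 14.5 (TSR-6) asks about detoxification, inpatient, outpatient and medication-assisted services over 28 days at each 4-weekly visit.
- Section 9.1.6 allows record abstraction as needed, to 52 weeks after randomization, and lists opioid overdose among the items abstracted.

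**Reporting route.**
- Section 15.2: "If non-fatal overdose resulted in a serious adverse event, it should also be captured on the AE/SAE CRF".
- Section 23.1 lists as a seriousness criterion: "Requires inpatient hospitalization or prolongation of existing hospitalization".
- Section 19.3.2 exempts admissions for detox, for labor and delivery, and for elective or pre-planned surgery. It then says: "The Lead Node will report all other SAEs on the Serious Adverse Event form in the data system".
- Section 19.5 says that "events related to complications of HIV, substance use treatment or admission for substance detoxification will be captured on study-specific forms" and are not to be reported a second time as an AE or SAE. It continues: "All hospitalizations for other (non-HIV, non-substance-use related) medical, surgical and psychological reasons and deaths will be reported on AE/SAE forms". It adds that the DSMB still receives these data.

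**The concern.** Section 24.2.5.5 names potentially life-threatening opioid intoxication as a study-specific risk and ties it to the end of a dosing interval and to missed doses. Both can occur well before week 20, yet the one question that asks about overdose directly does not reach back that far for a participant seen at week 24. Section 17.13 specifies no separate analysis of the overdose form.

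The reporting rules matter because the route decides what happens next. Section 23.4 requires reportable SAEs within 24 hours, Section 23.6.3 notifies the Medical Monitor of them, and Section 17.13 builds the by-arm tables from AEs and SAEs. No such timeline is stated for study-specific forms. If sites follow different sections, the same kind of hospitalization could appear in those tables from one site and not from another.

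**Working it through.** The plan states no coverage figure, so there is none to reproduce.

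**Part A: coverage of the structured question**

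Inputs: look-back of 4 weeks, asked once after baseline (Section 15.2); 24 weeks of follow-up with visits at weeks 4, 8, 12, 16, 20 and 24 (Sections 6.2 and 10.1). The baseline question looks back before randomization and adds nothing to follow-up coverage.

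1. Coverage for a participant seen at week 24 = look-back weeks / follow-up weeks = 4/24 = 16.7%.
2. Weeks without a structured question = 24 − 4 = 20; 20/24 = 83.3%.
3. The item is asked at 1 of the 6 scheduled 4-weekly visits.
4. For someone who leaves early and completes an end-of-study visit, the window is the 4 weeks before that visit, not weeks 20 to 24.
5. If the same 4-week item were asked at all six visits: 6 × 4 / 24 = 24/24 = 100%, provided that visits are attended about 4 weeks apart.
6. One since-randomization question at week 24 would also span 24 of 24 weeks.

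These are shares of follow-up time, not shares of overdoses detected. The documents give no overdose rate and no detection rate for the other routes.

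**Part B: reporting route, clause by clause**

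| Event | 19.3.2 with 23.1 | 15.2 | 19.5 |
|---|---|---|---|
| Hospitalization for an HIV complication | Serious and not among the three exemptions: SAE form | Not addressed | Study-specific form, not AE/SAE form |
| Hospitalization for non-fatal overdose | Serious and not among the three exemptions: SAE form | Overdose form and AE/SAE CRF | Not named; the parenthetical can be read to keep it off the AE/SAE form |
| Fatal overdose | SAE form | Not addressed (Section 15.3 sends it to the AE/SAE CRF) | Deaths go on AE/SAE forms |

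Row 1 is a direct contradiction. Row 2 depends on how the parenthetical in Section 19.5 is read. Row 3 is consistent.

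**The case against.** **On coverage.** Overdose is neither a primary nor a secondary outcome, and Section 10.0 deliberately limits assessments to contain burden. Capture is layered: AEs are solicited at every visit, all go on a paper log, TSR-6 asks about services every 4 weeks, and record abstraction names overdose. An event stays out of the data system only if it is both mild and unrelated. All of this stands, and it makes Part A an improvement rather than an error. It does not close the gap, because none of these routes asks the participant about overdose. Section 10.0 also allows assessments needed for safety. If the displaced schedule mark really means as needed, the form could be completed for a reported event, but there would still be no scheduled question at weeks 4 to 20.

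A reader might infer that five-sixths of overdoses would be missed, or that the arm comparison would be biased. The documents do not support either inference: 83.3% is uncovered time for one instrument, and the other routes can catch events in that time.

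**On reporting.** A reader might infer that Section 19.5 flatly overrides Section 15.2 for overdose. It does not name overdose. Its parenthetical may be shorthand for the list in its preceding sentence, and Section 15.2 is the more specific rule. A reader might also infer that nothing in the protocol settles the routing. That cannot be asserted, because the content of the Section 23.10 reporting chart is not in the extracted text and may bear on it. Nor do the documents support a claim that the DSMB loses these data, since Section 19.5 says it receives them. What stands is that the sentences on HIV-related hospitalizations contradict each other as written, whatever the chart shows.

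**Conclusion.** **Part A holds as a cheap safety improvement.** Structured coverage is 4 of 24 weeks (16.7%) for a participant seen at week 24. The exposed case is narrow: an overdose outside the look-back window that has no medical contact and is not volunteered. How many such events would occur cannot be determined, nor whether they would differ by arm. This assumes that the schedule row matches the Section 15.2 text.

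**Part B is wrong as written for HIV-related hospitalizations**, where Section 19.5 and Section 19.3.2 (with Section 23.1) give different routes. For overdose hospitalizations it is an ambiguity that sites could resolve differently. The consequence is possible inconsistency in expedited reporting and in the Section 17.13 tables, not demonstrated loss of safety data.

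The two parts can compound. If a site reads Section 19.5 as covering overdose, an overdose admission at week 10 would depend on a form whose scheduled week-24 question does not look back that far.

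**What to change.** **(a) Coverage.** Keep the existing 4-week item unchanged, so that it still matches baseline, and ask it at the existing week 4, 8, 12, 16, 20 and 24 visits. Add one since-randomization question at week 24 or end of study to cover missed visits. Section 15.2 itself argues that overdoses are less prone to recall bias than other events, which supports the longer look-back. Summarize non-fatal overdose descriptively by arm (number and proportion with at least one).

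Cost: the minimum version, the single added question, is 1 × 350 = 350 items. The full version is at most (5 + 1) × 350 = 2,100 short items, at visits that already collect the TLFB. Either version needs a CRF change, and the full one also changes the visit schedule; the added participant burden is small.

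**(b) Reporting.** Reconcile Section 19.5 with Sections 15.2, 19.3.2 and 23.1 and the Section 23.10 chart, so that one stated route for HIV-related and for overdose hospitalizations applies at all sites and the Section 17.13 tables are built consistently. Cost: one reconciled paragraph, a check of the chart and a note to sites. Depending on the route chosen, there may be more SAE forms to complete.
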